Adherence is essential for initial weight loss and long-term weight maintenance. It is unclear whether adherence to dietary protocols differs between lean and obese individuals and whether non-adherence is specific to weight loss intervention diets (compared to weight maintenance diets). Several predictors of adherence to medical treatments have been described, including associations with memory, problem solving, neuropsychological factors, personality traits and levels of motivation. To understand how adherence may differ by adiposity and diet, we will examine differences in dietary adherence between lean and obese individuals and within the obese group between those prescribed a heart-healthy weight maintenance versus reduced calorie

diet. We will also examine predictors of adherence and the relationship between dietary adherence and weight loss.

B. AIMS

The primary goal of the current study is to determine whether or not there are differences in dietary adherence between lean and obese individuals and between two groups of obese individuals assigned different heart-healthy dietary prescriptions (weight maintaining diet [WMEN] vs. underfeeding [UF]). Thus 3 groups will be compared:

1. Lean WMEN
2. Obese WMEN
3. Obese UF

The secondary aim is to:

1. Examine predictors of adherence in general (e.g. motivation, self-efficacy, social support, personality traits, stress, neuropsychological/cognitive factors)

C. HYPOTHESES

The primary hypothesis for the study is that:

1. Adherence to a heart-healthy dietary intervention will be greatest in the lean WMEN group, followed by the WMEN obese group, and subsequently lowest in the UF obese group

The secondary hypotheses are that:

1. Within the UF group, individuals with higher adherence scores will lose more weight than those with lower scores

2. Poor performance on neuropsychological tests and problem solving questionnaires will be associated with decreased adherence across all groups
3. Higher levels of neuroticism will be associated with lower levels of dietary adherence in all 3 groups
4. Higher levels of motivation and self-efficacy will predict greater adherence

D. RESEARCH DESIGN & METHODS:

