- Go/No Go Task (45): to examine inhibitory control. Subjects are required to press a key whenever a target stimulus is presented and to refrain from pressing the key when a non-target stimulus is presented
 - Meeting with study counselor: The counselor will review the weight-maintenance heart-healthy dietary prescription and provide the volunteer with 3 days of food. The volunteer will be instructed to eat only the foods provided, consume no additional foods, maintain their current levels of physical activity, and to keep track on a self-monitoring food record form.
 - Weight Maintenance Dietary Prescriptions:
 - Recent studies have found that using free prepared meals facilitated greater adherence (16) and weight loss compared with a control group (17). Therefore, because the primary aim of our study is to compare differences between lean and obese groups and WMEN versus UF diets (rather than investigate real-world learning), all food items will be provided by the CRU, primarily as prepackaged meals and snacks for the volunteers to take home (see Table 2 for sample menu).
 - All diets will have 20%, 30%, and 50% of daily calories provided as protein, fat and carbohydrate, respectively. They are designated as "heart-healthy" because they will be balanced diets, which are also low in cholesterol and saturated fat.
 - During the baseline week, all participants will be fed their weight maintaining energy needs (WMEN), equal to the number of calories calculated for each participant based on the WHO equation with an activity factor (1.3-1.5)(46;47), based on results from the PAR questionnaire.

- *Women:* 18 to 30 y: $EE = 13.3 \times \text{weight (kg)} + 344 \times \text{height (m)} + 35$
30 to 60 y: $EE = 8.7 \times \text{weight (kg)} - 25 \times \text{height (m)} + 865$
- *Men:* 18 to 30 y: $EE = 15.4 \times \text{weight (kg)} - 27 \times \text{height (m)} + 717$
30 to 60 y: $EE = 11.3 \times \text{weight (kg)} + 16 \times \text{height (m)} + 901$
- During the first week, and prior to randomization, all patients will come for 2 outpatient visits to be weighed
- If their weight changes by 2%, their caloric intake will be adjusted by 200 kcal accordingly

Baseline Visit 2:

1. Weight
2. Adjust calories by 2%, if needed

Outpatient Visits (6 weeks):

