For our primary hypothesis, a one-way ANOVA will be performed with total adherence score as the dependent variable and group status (lean WMEN, obese WMEN, obese UF) as the independent variable. In addition, linear regression models adjusted for covariates including age, sex, race, socioeconomic status (SES) and baseline weight or percent body fat will also be used to examine the relationship of adherence and behavioral factors. Correlations between adherence scores, behavioral test scores and weight, fat mass and fat free mass loss will be calculated. Pearson's r will be calculated for data that are normally distributed and Spearman's correlation will be used if the distributions are non-normal. This will be an intention to treat study such that everyone who completes the run-in phase will be included in the final analysis. Missing data will be completed using a multiple imputation method utilizing the SAS procedures, PROC MI and MIANALYZE. This method introduces variability into the imputed values to reduce the risk of a type 1 error. All tests will have a 2-sided Type I error of $p = 0.05$.

Power Calculation:

Sample size calculations are based on the number of individuals needed to demonstrate a significant difference in adherence scores over the 6-week intervention period between the 3 diet groups (lean WMEN, obese WMEN, obese UF).

We based our expected percent adherence score on a recent paper by Williamson et al (26) who observed 52% adherence in a group of obese dieters. Our maximum possible adherence score is 21 per week. To account for the increased adherence we expect to see because food is being provided in the study, we have increased the proposed adherence from the 52%

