adherence observed in the POUNDS LOST study by an additional 10% and applied this increase in score across all 3 groups. Thus, assuming 62% adherence, we would expect a mean weekly score of 13 in the calorie restricted group. If we in addition, consider a smaller a meaningful difference between the groups of 3 points; (lean WMEN = 19, obese WMEN = 16, obese UF = 13), assuming the same SD = 6, with a calculated sum of squares of the means = 32, across 3 treatment groups with a mean 16 +/- SD = 6, alpha = 0.05, the proposed total of 20 subjects per group (total n = 60) would allow us to achieve a power of 0.793 (**see table 3a**). If we assume a larger difference between the groups 3.5 points; lean WMEN = 20, obese WMEN = 16.5, obese UF = 13), the proposed total of 20 subjects per group (total n = 60) would allow us to achieve a power of 0.906 (**see Table 3a**). Because the drop-out rate in weight loss intervention studies averages around 25%, we plan to recruit a total of 150 subjects (25 per group) to account for both screening failures and attrition, and to ensure 60 completers (**see Table 3b**).

7. Benefits:

This is a supervised dietary outpatient study being offered to lean and overweight/obese individuals. The prescribed diet is "Heart-healthy" and could improve metabolic and health outcomes in all 3 groups. In addition, those in the UF group who adhere to the diet may experience weight loss, which may lead to additional favorable future metabolic outcomes. All volunteers will receive information regarding some aspects of their health, including lab screening tests, a thorough physical examination, a measure of body fat, and an evaluation of their glucose tolerance status. The results of these tests will be available to the subjects and will be provided to their personal physician, if desired. Other expected benefits of this study include obtaining generalizable knowledge related to the difference in levels of adherence between lean

and overweight/obese individuals, which has not yet been examined. We will also gain knowledge about predictors of treatment adherence for weight loss and the relationship between adherence and weight loss. Moreover, we are proposing novel ways to measure adherence, which could be used in future studies. The information obtained from this study should be useful to scientists, physicians, and psychologists.

8. Human Subjects Precautions:

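### The test of adherence against weight loss in the underfed group states no scale and no adjustment, although the prescribed deficit differs between participants by design

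*Combined protocol and SAP*

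**What the plan says.** Section C, secondary hypothesis 1: "Within the UF group, individuals with higher adherence scores will lose more weight than those with lower scores". The claim is confined to one arm.

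Section D.6, Statistical Analysis, gives the only analysis of weight loss: "Correlations between adherence scores, behavioral test scores and weight, fat mass and fat free mass loss will be calculated". Pearson or Spearman is chosen according to normality. The sentence does not say whether loss is in kilograms or in percent, names no covariate and does not restrict itself to the UF group. The sentence before it lists regressions adjusted for age, sex, race, SES and baseline weight or percent body fat, but these are for adherence and behavioral factors, not for weight loss.

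Section D.4, Weight Maintenance Dietary Prescriptions, sets energy needs as "equal to the number of calories calculated for each participant based on the WHO equation with an activity factor (1.3-1.5", with separate equations by sex and age band, all rising with weight. The UF diet is a percentage of those needs in both places where it is described. The opening summary puts it 35% below needs, and the Randomization item in D.4 puts it at 35% of needs. These two statements conflict and must be reconciled.

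Section D.6, Power Calculation, covers the primary ANOVA only: "the proposed total of 20 subjects per group (total n = 60) would allow us to achieve a power of 0.793", with means "lean WMEN = 19, obese WMEN = 16, obese UF = 13" and "assuming the same SD = 6". No power is given for the correlation.

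**The concern.** A percentage prescription gives a larger absolute deficit to people with larger needs. Two UF participants who follow the diet equally well are therefore expected to lose different numbers of kilograms. An unadjusted correlation of the adherence score with kilograms lost treats that designed difference as unexplained variation.

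If adherence is unrelated to sex and size, the result is attenuation and some lost power. If it is related, the correlation is confounded: upward when larger participants adhere better, downward when they adhere worse.

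At stake is the plan's only test of whether adherence translates into weight loss, in about 20 people. Because the scale is not stated, it could also be chosen after the data are seen.

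**Working it through.** **1. The plan's own figure.** For a one-way ANOVA, λ = n·Σ(μᵢ − μ̄)²/SD². With means 13, 16, 19, SD 6 and n = 20, λ = 20 × (9 + 0 + 9)/36 = 10, giving power 0.7933 against the stated 0.793. With means 13, 16.5, 20, λ = 20 × 24.5/36 = 13.6, giving 0.9059 against the stated 0.906. Both reproduce. Neither concerns the weight-loss correlation. At two-sided 0.05 and 80% power, the smallest detectable correlation is 0.59 at n = 20 and 0.67 at n = 15.

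**2. Spread of the prescribed deficit.** Needs = equation × activity factor. Examples use age 40 and factor 1.4:

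- Woman, 1.60 m, 80 kg: (8.7×80 − 25×1.60 + 865) × 1.4 = 1,521 × 1.4 = 2,129 kcal
- Man, 1.78 m, 155 kg: (11.3×155 + 16×1.78 + 901) × 1.4 = 2,681 × 1.4 = 3,753 kcal

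Read as 35% below needs, the deficits are 745 and 1,314 kcal/day. Read as 35% of needs, they are 1,384 and 2,440. The ratio is 1.76 either way, because the reading only multiplies every deficit by 65/35. These are near-extreme cases; for a correlation, the CV matters.

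A simulated UF group used the plan's equations, activity factor 1.3–1.5, 50% women and weight below 350 lb (158.8 kg). Assumed: age uniform 18–60 (the equations stop at 60), mean height 1.76 m for men and 1.62 m for women, mean BMI 35 with SD 3 or 5. The CV of needs was 16.5–17.2%, and the CV of needs per kg was 9–10%.

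**3. Effect on the correlation.** The plan's UF mean is 13 ("we would expect a mean weekly score of 13 in the calorie restricted group") with SD 6, so the adherence CV is 6/13 = 46%. It is 31% at SD 4 and 23% at SD 3. Assume loss = f × deficit, where f is the realised fraction of the deficit, has correlation r₀ with the score and is independent of body size. Then CV_f = CV_adherence/r₀, and

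r(raw) = r₀ · CV_f / √(CV_f² + CV_D² + CV_f²·CV_D²).

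At SD 6, r₀ = 0.6 and CV_D = 0.165: CV_f = 0.4615/0.6 = 0.769, and r(raw) = 0.6 × 0.769/√(0.5917 + 0.0272 + 0.0161) = 0.58.

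**4. Power at n = 20.** Fisher z, power ≈ Φ(atanh(r)·√(n−3) − 1.96). For r = 0.58: 0.6625 × 4.123 − 1.96 = 0.77, so power is 0.78. Partial correlations use n − 1. Ranges span the two BMI SDs.

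| r₀ | Adherence SD | Loss ÷ deficit | Loss in kg, unadjusted | Percent of baseline weight | kg, deficit as covariate |
|---|---|---|---|---|---|
| 0.6 | 6 | 0.815–0.816 | 0.775–0.779 | 0.802–0.804 | 0.776–0.778 |
| 0.6 | 4 | 0.813–0.816 | 0.742–0.751 | 0.789–0.794 | 0.774–0.778 |
| 0.6 | 3 | 0.813–0.816 | 0.705–0.709 | 0.777–0.778 | 0.774–0.777 |
| 0.7 | 6 | 0.946–0.947 | 0.913–0.917 | 0.936–0.938 | 0.923–0.924 |
| 0.7 | 4 | 0.946–0.947 | 0.884–0.888 | 0.927–0.929 | 0.924 |
| 0.7 | 3 | 0.946–0.947 | 0.835–0.847 | 0.911–0.918 | 0.922–0.925 |

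Measured against loss ÷ deficit, unadjusted kilograms cost 3–4 points at SD 6, 6–7 at SD 4 and 10–11 at SD 3.

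**5. Dependence on the model.** Separate simulations of trials of 20 compared unadjusted loss with deficit-adjusted loss. At SD 6, power rose from 0.76 to 0.80 (0.64 to 0.68 and 0.80 to 0.83 with added weight noise). The gain was about 7–13 points at SD 4 and about 21 at SD 3. A further run at SD 6 and r₀ = 0.6 gave 0.76 unadjusted, 0.81 with the covariate and 0.83 for loss ÷ deficit. So at SD 6 the covariate recovers anywhere from nothing (table) to about 5 points.

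**The case against.** The strongest case against the point has five parts.

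- **Kilograms are not stated.** A reader might infer that the plan chose unadjusted kilograms. It did not; it is silent. The Introduction reports weight loss in an earlier diet comparison as a percent of body weight, so the percent scale is familiar to the authors. This stands: the defect is a missing specification.
- **The effect is small on the plan's own SD.** A reader might infer a large power loss, such as 0.66 against 0.84. That result needs a narrow adherence spread: assumed extra intake of mean 300 and SD 200 kcal/day, with mean needs of 2,786 kcal and a 35% deficit. The CV of the realised deficit is then 200/(975 − 300) = 30%, against 46% from the plan's 6/13. This stands at SD 6. However, on a 0–21 scale a group with mean 20, as in the plan's second scenario, cannot have an SD above √(20×1) = 4.47. A common SD of 6 is therefore doubtful, although not impossible at a mean of 13.
- **The 35%-of-needs reading is not worse in itself.** Much larger losses appear under it only if extra intake stays fixed in kcal while the deficit nearly doubles. With the realised fraction held constant, the correlations do not change. This stands.
- **Percent loss recovers much of the cost.** It does, and in the table it matches or beats the covariate form at SD 3 to 6 when r₀ = 0.6. It is incomplete because needs per kg fall as weight rises. Adjusting for baseline weight alone gives 0.767–0.770 at SD 6 and r₀ = 0.6, no better than no adjustment.
- **Attenuation is not certain.** All these runs take adherence as independent of size. If larger participants adhere better, unadjusted kilograms would inflate the correlation. This stands, and it is a reason to adjust rather than to leave the test alone.

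**Conclusion.** The point holds as a specification gap in a secondary analysis. The plan names no scale, covariate or analysis group for the test of secondary hypothesis 1, while its own prescription rule makes the expected loss at equal adherence differ between participants.

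If loss is analysed in kilograms without adjustment, the power cost at n = 20 is about 3–5 points at the plan's SD of 6. It is roughly 7–20 points at an adherence SD of 3–4, where the upper end comes from less favourable simulation assumptions. These figures rest on an assumed true correlation of 0.6–0.7, loss proportional to deficit, and adherence independent of size. If adherence depends on sex or size, bias in either direction is the larger worry.

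The documents do not support reading this as a large, certain loss of power or as a threat to the main result. The primary ANOVA does not use weight loss and is unaffected.

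**What to change.** In section D.6, state that secondary hypothesis 1 is tested in the UF group by regressing weight change, from the randomisation-visit weight, on the adherence score with each participant's prescribed daily deficit (kcal) as covariate. Do the same for fat mass and fat-free mass, with change measured from the baseline DXA. Report the unadjusted correlation and percent-of-baseline-weight loss as supportive.

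Prespecify this one form. Loss divided by predicted loss is a different model with different residual assumptions, so it should not be offered as interchangeable. The covariate form does not require loss to be strictly proportional to the deficit, and it addresses confounding through the deficit. Its power gain at SD 6 may be slight, so the case for it rests mainly on removing that confounding and on fixing the analysis in advance.

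The two descriptions of the UF percentage must be reconciled so that the covariate is defined.

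Cost: a short addition to the analysis section and one degree of freedom. No new data are needed, because the prescribed deficit follows from the needs already calculated to set each diet.

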The design of this study will allow us to look at differences in levels of adherence to a heart-healthy dietary prescription in lean vs. obese individuals. We will also be able to compare adherence levels in obese individuals who are being fed a WMEN diet compared to an UF diet. Additionally, we will measure predictors of adherence and the relationship between adherence and weight loss.

Data Analysis:

Measuring Adherence: (see Appendix B): for all measures, adherence will be examined as a binary variable (adherent versus non-adherent). Each measure will be awarded 0 points if non-adherent and 1 point if adherent.

1. Attendance: two sessions per week: (adherent = attended; non-adherent = not attended; 12 possible total points over the study).
 - a. counseling
 - b. food pick-up
2. Food Diaries: volunteers will turn in diaries during their weekly counseling visit. For each weekly diary there will be three scores (18 possible total points over the study):
 - a. *Completion of records*: adherent = completed diary; non-adherent = missing or incomplete diaries
 - b. *Dietary Adherence to Foods provided*: adherent = consumed all; non-adherent = did not consume all
 - c. *Adherence to Additional Foods*: adherent = did not consume any; non-adherent = consumed additional foods
3. 24-hour recall in-person interview: once per week on day of counseling session. For each session there will be three scores (18 possible total points over the study):
 - a. *Completion of interview*: adherent = completed interview; non-adherent = did not complete interview
 - b. *Dietary Adherence to Foods provided*: adherent = consumed all; non-adherent = did not consume all
 - c. *Adherence to Additional Foods*: adherent = did not consume any; non-adherent = consumed additional foods

4. 24-hour recall using computerized confessional: once per week on day of counseling session. For each session there will be three scores (18 possible total points over the study):
 - a. *Completion of records*: adherent = completed interview; non-adherent = did not complete interview
 - b. *Dietary Adherence to Foods provided*: adherent = consumed all; non-adherent = did not consume all
 - c. *Adherence to Additional Foods*: adherent = did not consume any; non-adherent = consumed additional foods
5. 24-hour recall (telephone): once per week. For each phone session there will be three scores (18 possible total points)

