 - a. *Completion of recall*: adherent = completed recall; non-adherent = did not complete recall
 - b. *Dietary Adherence to Foods provided*: adherent = consumed all; non-adherent = did not consume all
 - c. *Adherence to Additional Foods*: adherent = did not consume any; non-adherent = consumed additional foods
6. EMA recordings: there will be two contacts per day. For each contact there will be three adherence scores. To avoid having EMA be more heavily weighted in the total score, the total weekly score will be divided by 7 to obtain an average weekly EMA score (42 possible total points per week; 6 possible total average points):

- a. *Completion of recording*: adherent = completed recording; non-adherent = did not complete recording. We will define incomplete or missing entries as non-adherent for that day.
 - b. *Dietary Adherence to Foods provided*: adherent = consumed all; non-adherent = did not consume all
 - c. *Adherence to Additional Foods*: adherent = did not consume any; non-adherent = consumed additional foods
7. Additional Non-Intervention Related Adherence Measure (once per week. For each rating there will be 1 score (6 possible total points over the study): We will also track the arrival time for weekly counseling session as a measure of adherence that is not directly related to the study intervention. Appointment adherence will be scored as the arrival within 5 minutes of the scheduled time and actual arrival time will be documented as a continuous measure of adherence. This measurement will allow us to examine the relationship between adherence to the dietary protocol and adherence to "other" factors (e.g. punctuality) and it will be included in the total adherence score.
- a. Appointment adherence: adherent = arrived within 5 minutes of scheduled appointment; non-adherent = did not arrive within 5 minutes of scheduled appointment

Adherence Score: The above variables will be totaled up to calculate a total adherence score out of a possible 21 points during each week. A percent (%) adherence score will also be calculated by dividing the total score by the number of variables assessed (21) and multiplying by 100 ($[(\text{total}/21)*100]$).

Statistical Analysis:

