8.1. Recruitment and Minority Participation

Participants will be recruited via advertising in local newspapers and on the internet, strategies which have proved successful in the past. Based on our previous studies, we expect the ethnic diversity of our volunteers to be approximately 40% Caucasian, 40% Native American, 10% Black and 10% Hispanic. Native Americans represent approximately 2% of the population in greater Phoenix area, and we anticipate over-representation because our unit is situated within the Phoenix Indian Medical Center. Additionally, Native Americans have previously participated in many of our studies. We anticipate recruiting approximately 5 volunteers per month (60/year) over the course of about 1.5 years.

8.2. Safeguards for subjects:

Subjects will have the option of discontinuing the study at any time. All data will be treated confidentially, and the identity of subjects will not be disclosed in publications. Participants will be monitored (weight and blood pressure) and seen by a counselor weekly. Any participant judged on clinical grounds to have suffered any adverse effect will be evaluated by a provider (physician, physician assistant, nurse practitioner, or psychologist).

8.3. Risks and Discomforts:

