| ▪ Food Diary food supplied | 0 | | | | | |
| ▪ Food diary consuming other food | 0 | | | | | |
| ▪ 24-hr recall interview completed | 1 | | | | | |
| ▪ 24-hr recall interview food supplied | 1 | | | | | |
| ▪ 24-h recall interview consuming other foods | 0 | | | | | |
| ▪ Computer confessional completed | 1 | | | | | |
| ▪ Computer confessional food supplied | 1 | | | | | |
| ▪ Computer confessional consuming other food | 0 | | | | | |
| Session Attendance (#2: wt, food pick-up) | 1 | | | | | |
| 24-hr recall phone completion (1) | 1 | | | | | |
| 24-hr recall phone food supplied (1) | 1 | | | | | |
| 24-h recall phone consuming other foods (1) | 0 | | | | | |
| EMA daily completion of records (1) | 7 | | | | | |
| EMA daily adherence of foods supplied (1) | 6 | | | | | |
| EMA daily adherence of consuming other foods (1) | 4 | | | | | |
| EMA daily completion of records (2) | 5 | | | | | |
| EMA daily adherence of foods supplied (2) | 5 | | | | | |
| EMA daily adherence of consuming other foods (2) | 2 | | | | | |
| AVERAGE weekly EMA Score (total possible = 6) | 4.1 | | | | | |
| On Time Arrival for Session | 1 | | | | | |
| Total Score | 13.1 | | | | | |
| % Adherence (total/21) *100 | 62% | | | | | |

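### Does the primary adherence score lack a rule for weeks after drop-out, given that missing data are to be multiply imputed?

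*Combined protocol and SAP*

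**What the plan says.** All references are to the combined protocol and SAP.

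- **Population (D.6, Statistical Analysis).** The analysis is labelled intention to treat, and "everyone who completes the run-in phase will be included in the final analysis". Anyone who leaves during the six intervention weeks stays in the ANOVA.
- **Missing data (same paragraph).** "Missing data will be completed using a multiple imputation method utilizing the SAS procedures, PROC MI and MIANALYZE". No variables, level (item, week or total), model or number of imputations are given.
- **Item scoring (D.6, Measuring Adherence).** Attendance is "adherent = attended; non-adherent = not attended; 12 possible total points over the study". Diary completion has "non-adherent = missing or incomplete diaries". Recalls not completed are non-adherent. For the smart-phone recordings, "We will define incomplete or missing entries as non-adherent for that day".
- **Total (D.6, Adherence Score).** A "total adherence score out of a possible 21 points during each week", with the percentage always taken over 21.
- **Sample score sheet.** In the worked week the diary was not completed, and the dependent row reads "Food Diary food supplied | 0"; the row for other foods is also 0.
- **Leaving the study (8.2).** "Subjects will have the option of discontinuing the study at any time". Section 8.7 foresees non-completion for illness, family emergency or noncompliance.

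**The concern.** Two rules seem to claim the same weeks. If a participant leaves after week 3, the item rules read literally give 0 for weeks 4 to 6, because sessions were not attended and records not completed. The imputation sentence read literally fills those weeks in. The first counts leaving as non-adherence. The second estimates what adherence would have been had the person stayed. These are different quantities for the primary outcome, and a choice left unwritten could be made after the data are seen.

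The difference is not small for one person. Someone scoring 16 a week who leaves after week 3 has a mean weekly score of 16 × 3/6 = 8 under the first rule and stays near 16 under the second. If leaving is commoner in one group, the group comparison shifts as well.

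**Working it through.** **1. The plan's own power.** Inputs from D.6, Power Calculation: means 19/16/13, SD 6, 20 per group, alpha 0.05. The squared deviations of the means sum to 9 + 0 + 9 = 18. The noncentrality is 20 × 18/36 = 10, and with 2 and 57 degrees of freedom the power is 0.793, as in Table 3A. At 25 per group it is 25 × 18/36 = 12.5, power 0.883.

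**2. Do the scoring rules leave a blank?** The weekly maximum is 2 (attendance) + 3 (diary) + 3 (interview) + 3 (computer) + 3 (telephone) + 6 (smart-phone) + 1 (punctuality) = 21. In the sample week:

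- attendance 2, diary 0, interview 2, computer 2, telephone 2, punctuality 1: sum 9
- smart-phone (7 + 6 + 4 + 5 + 5 + 2)/7 = 29/7 = 4.1
- total 13.1, and 13.1/21 = 62%, as printed.

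The uncompleted diary costs all three points and the denominator stays 21. Had the two dependent diary items been treated as missing, the result would have been 13.1/19 = 69%. The sheet therefore scores absence as 0 and does not set it aside. Attendance also has a fixed 12 points over the study. On these rules a total exists for every participant, including one who left.

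**3. What the choice moves.** The group mean with later weeks scored 0 is m × [1 − p(1 − k/6)] for drop-out fraction p after week k. Uniform timing over weeks 1 to 5 has mean k = 3, so the factor is 1 − p/2. Assumptions: the planning means describe adherence while on study, scores are normal, drop-out is equal across groups and unrelated to adherence, 25 per group. Power is from 40,000 simulated trials per row.

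| Drop-out | Zero-scored means | Power, zero-scored | Power, imputed |
|---|---|---|---|
| 5% | 18.5 / 15.6 / 12.7 | 0.84 | 0.88 |
| 10% | 18.1 / 15.2 / 12.4 | 0.79 | 0.88 |
| 25% | 16.6 / 14.0 / 11.4 | 0.67 | 0.88 |

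The order of the groups does not change. Capping scores at 0 and 21, which the plan's SD makes relevant, gives 0.58 against 0.86 at 25%.

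**4. Unequal drop-out with equal adherence of 16 (after week 3, lean / obese WMEN / obese UF).** At 5/10/15% the zero-scored means are 15.6/15.2/14.8 and the test rejects in about 6.5% of trials. At 10/25/40% they are 15.2/14.0/12.8 and it rejects in about 20%. Imputation gives 5% in both cases. If leaving is meant to count as non-adherence, the excess is a true difference in that outcome and not a false positive.

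**The case for a change.** The strongest case for a change is that the imputation sentence is unrestricted, so it also permits imputing the total score from group alone. Suppose people leave after week 3 because their early scores are low (a common cut-off of 11.5 on the mean of weeks 1 to 3, an assumed week-to-week correlation of 0.7, drop-out of 11/23/40%). At 25 per group, the planned lean-to-UF gap of 6.0 becomes 3.5 under that procedure, with power 0.48. Section 8.7 foresees discontinuation for noncompliance, so drop-out linked to adherence is plausible.

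The arithmetic stands; its link to this plan is weak. The plan does not describe group-only imputation. The weekly scores are recorded on the score sheet, and an analyst using PROC MI would be expected to put them in the model. In the same scenario the two reasonable handlings almost agree on power: 0.86 zero-scored (gap 7.0) and 0.88 imputed with earlier weeks (gap 6.0).

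It also stands that the text is incomplete in two places. Nothing mentions weeks after discontinuation, and for the two food items of an uncompleted recall the zero is only inferred from the diary rows of the sample sheet.

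The larger effects need about 25% drop-out after the run-in. The Power Calculation cites that rate for weight-loss studies. Here two of three groups maintain weight, the intervention lasts six weeks, all food is supplied, and $575 of the $625 is paid at completion. The documents give no drop-out figure by group.

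**Conclusion.** This is a gap that analysts can fill sensibly from the text. The item rules and fixed totals give a value to sessions and records that did not happen. The imputation sentence still has work to do on data that can be blank: questionnaires (section 8.3.e lets participants skip questions), covariates, weight and DXA. Read together, the rules do not collide.

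Neither way of treating later weeks is wrong. Zero-scoring charges illness or a family emergency as non-adherence, and imputation credits adherence to people who left. Preferring one would trade one fair estimand for another.

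With equal drop-out of 5 to 10% the choice costs roughly 0.04 to 0.09 in power (0.88 against 0.84 and 0.79); at 25% it costs about 0.21. These figures rest on assumed drop-out rates, timing and normal scores, and on reading the planning means as on-study adherence. If those means already count drop-outs as 0, zero-scoring loses no power. The point is missing detail of low to moderate weight, not a demonstrated error, and the plan need not change.
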